#### 8.1.3.4.3 Management Guidelines for Eye Toxicity Associated With Vision Changes

Eye toxicities considered a consequence of dry eye should be managed as per the standard clinical practice and as per the standard toxicity management guidelines described in the protocol. Subjects with confirmed new corneal or retinal abnormality while taking the study medication should be reported with an AE of special interest (Grade 1 and 2) or SAE (Grade  $\geq 3$ ) as appropriate.

Any new eye symptoms of clinical significance such as but not limited to blurred vision, partial or complete loss of vision, double vision, floaters or color spots or halos around light, change in color or night vision, photophobia, ocular pain or stinging sensation, and foreign body sensation should be further evaluated and managed as per the Dose Modification guidelines for ocular toxicity (Section 8.4).

#### 8.1.3.4.4 Guidelines for the management of dry eye

- General considerations: Avoid unnecessary exposure to sunlight, use sunglasses in bright light.
- Prophylactic management: Frequent use of artificial tear substitutes is strongly recommended.
- Reactive management:
  - Withhold erdafitinib for Grade 3 toxicity
  - Artificial tear substitutes if not started, every 4 to 6 hours
  - Hydrating /lubricating eye gels and ointments
  - Severe treatment-related dry eye should be evaluated by an Ophthalmologist

## 8.2 Fulvestrant

### 8.2.1 Most common anticipated toxicities (refer to package insert for further details)

- Hot flashes
- Joint disturbances
- Injection site reactions
- GI disturbances

There is considerable clinical experience with fulvestrant 500 mg intramuscular dosing every 4 weeks (with an initial loading dose phase at cycle 1 day 15); it is generally very well tolerated. As was clearly established in the CONFIRM trial, the higher dose of fulvestrant 500 mg is more efficacious than the lower dose of 250 mg, with essentially no difference in adverse event rates. Dose reduction to 250 mg is left to the discretion of the treating physician, but it is not anticipated that dose reduction will improve adverse effects and it should generally be avoided given the inferior efficacy. However, dose reduction to fulvestrant 250 mg can be considered in patients with moderate hepatic impairment.

## 8.3 Palbociclib

### 8.3.1 Most common anticipated toxicities (refer to package insert for further details)

- Neutropenia
- Leukopenia
- Anemia
- Thrombocytopenia
- Fatigue
- Nausea

The primary anticipated toxicity of palbociclib is neutropenia. In the phase I trials of palbociclib alone in patients with advanced cancers, neutropenia was the only dose-limiting toxicity (DLT). Grade 3 neutropenia during cycle 1 was observed in 3/22 patients receiving palbociclib 125 mg PO daily, with no grade 4 neutropenic events observed. Based on this result, 125 mg PO daily became the recommended phase II dose (RP2D). Other hematologic AEs of grade 3 or greater during cycle 1 were anemia and leukopenia, occurring in 1 and 4 of 41 patients, respectively. The most common non-hematologic AEs of grade 3 or greater during cycle 1 were fatigue, nausea, and abdominal pain (each occurring in 2 of 41 patients). Of note, there were no complicated hematologic AEs documented, and all hematological AEs resolved during the off drug period of a 3 week on/1 week off schedule, and were non-cumulative.

In a phase II trial of palbociclib alone for advanced breast cancer, the only toxicities grade  $\geq 3$  observed were transient neutropenia (50%) and thrombocytopenia (21%). In a phase II trial of palbociclib plus letrozole for first-line therapy of ER+ MBC, the most common AEs reported were neutropenia, leukopenia, and fatigue. The median time to first treatment delay for neutropenia was 58 days, and the median duration of treatment delay until recovery was 5 days (range 1-16 days). In general, hematological abnormalities were adequately managed with standard supportive care, were not complicated, and resolved during the drug hold with no cumulative toxicity noted. In the phase I dose-escalation trial of palbociclib alone, QT interval changes were also evaluated in detail. While 26 of 41 patients had a maximum increase of <30 msec from baseline QTc, no patients had an on-treatment value exceeding 500 msec.

### 8.3.2 Dose Modification/ Delays and Toxicity Management

In the event of significant treatment-related toxicity, palbociclib and erdafitinib dosing may be interrupted or delayed and/or reduced as described below. In the event of multiple toxicities, dose modification should be based on the worst toxicity observed. Patients are to be instructed to notify investigators at the first occurrence of any adverse sign or symptom. Patients should not hold or discontinue palbociclib and erdafitinib for side effects potentially or likely related to concomitant anti-hormonal therapy (e.g., grade 3 or long lasting grade 2 joint pain) as per the investigator's judgment.

Missed doses are not made up. When the adverse event resolves, the cycle will continue as scheduled. However, if palbociclib or erdafitinib start for a specific cycle is delayed for toxicity, fulvestrant will continue without change.

The need for a dose reduction at the time of treatment resumption should be based on the table criteria below unless expressly agreed otherwise following discussion between the investigator and the Protocol Chair. If a dose reduction is applied, the patient may need to return to the clinic to receive new drug supply.

### 8.4 Palbociclib and Erdafitinib Dose Modifications and Management of Toxicities

Palbociclib dose level reductions							
Starting dose	First reduction	Second reduction	Third reduction				
125 mg	100 mg	75 mg	Discontinue if no clinical benefit has been seen				
Erdafitinib dose level reductions							
Starting dose	First reduction	Second reduction	Third reduction	Fourth reduction			
8 mg	6 mg	5 mg	4 mg	Discontinue if no clinical benefit has been seen			
6 mg	5 mg	4 mg		Discontinue if no clinical benefit has been seen			
5 mg	4 mg	Discontinue if no clinical benefit has been seen					
Investigations – Hematology (for palbociclib only)							
ANC decreased (Neutropenia)							
Grade 1 / 2	Maintain dose level of palbociclib.						
Grade 3	Omit dose of palbociclib until ANC $\geq$ 1000/mm  , then 
 
- If resolved in <math>\leq</math> 7 days, then maintain dose level of palbociclib.
 
- If resolved in <math>></math> 7 days, then <math>\downarrow</math> 1 dose level of palbociclib.
 
						
Grade 4	Omit dose of palbociclib until ANC $\geq$ 1000/mm  , then $\downarrow$ 1 dose level of palbociclib. Erdafitinib should be omitted as well if the treating physician considers that the safety of the patient is compromised.						
Anemia							
Grade 1 / 2	Maintain dose level of palbociclib.						
Grade 3	Omit dose of palbociclib until resolved to CTCAE Grade $\leq$ 2, then maintain dose level of palbociclib						
Grade 4	Discontinue palbociclib.						
Febrile neutropenia							
Grade 3	Omit dose of palbociclib, then						

	
 
- If resolved by <math>\leq</math> 7 days, then, <math>\downarrow</math> 1 dose level of palbociclib.
 
- If not resolved within 7 days discontinue palbociclib.
 

Grade 4	Discontinue palbociclib. Erdafitinib should be omitted as well if the treating physician considers that the safety of the patient is compromised.
Platelet count decreased (Thrombocytopenia)	
Grade 1 / 2	Maintain dose level of palbociclib.
Grade 3	
 
Omit dose of palbociclib until resolved to CTCAE Grade <math>\leq</math> 1, then                     
 
- If resolved in <math>\leq</math> 7 days, then <math>\downarrow</math> 1 dose level of palbociclib.
 
- If resolved in <math>></math> 7 days and/or with signs of bleeding, then discontinue patient from palbociclib.
 
 
 

Grade 4	Discontinue palbociclib.
Bleeding	
Any bleeding (related to palbociclib) resulting in platelet transfusion	Omit dose of palbociclib until no further bleeding has been observed. Continuation of study treatment may be considered based on the thrombocytopenia recommendations.
Investigations – Hepatic	
Total bilirubin (for patients with Gilbert syndrome these dose modifications apply to changes in direct bilirubin only)	
Grade 1	Maintain dose level of palbociclib and erdafitinib.
Grade 2	
 
Omit dose of palbociclib and erdafitinib, and check bilirubin daily until resolved to CTCAE Grade <math>\leq</math> 1, then:                     
 
- If resolved in <math>\leq</math> 7 days, then maintain dose level of palbociclib and erdafitinib.
 
- If resolved in <math>></math> 7 days, then <math>\downarrow</math> 1 dose level of palbociclib and erdafitinib. Start palbociclib first, and recheck bilirubin level in 7 days. If level remains CTCAE Grade <math>\leq</math> 1, then reintroduce erdafitinib.
 
 
 

Grade $\geq$ 3	Discontinue palbociclib and erdafitinib.
Note: If CTCAE Grade 3 or 4 hyper-bilirubinemia is due to the indirect (non-conjugated) component only, and hemolysis as the etiology has been ruled out as per institutional guidelines (e.g. review of peripheral blood smear and haptoglobin determination), then $\downarrow$ 1 dose level of palbociclib and erdafitinib and continue treatment at the discretion of the Investigator.	
AST or ALT	
Grade 1	Maintain dose level of palbociclib and erdafitinib.
Grade 2	
 
Omit dose of palbociclib and erdafitinib, and check AST and ALT daily until resolved to CTCAE Grade <math>\leq</math> 1, then                     
 
- If resolved in <math>\leq</math> 7 days, then maintain dose level of palbociclib and erdafitinib
 
- If resolved in <math>></math> 7 days, then <math>\downarrow</math> 1 dose level of palbociclib and erdafitinib. Start palbociclib first, and recheck AST and ALT levels in 7 days. If levels remain CTCAE Grade <math>\leq</math> 1, then reintroduce erdafitinib.
 
 
 

Grade 3	
 
Omit dose of palbociclib and erdafitinib, and check AST and ALT daily until resolved to CTCAE Grade <math>\leq</math> 1 (or CTCAE Grade <math>\leq</math> 2 in case of liver metastasis), then                     
 
- If resolved in <math>\leq</math> 7 days, then <math>\downarrow</math> 1 dose level of palbociclib and erdafitinib. Start palbociclib first, and recheck AST and ALT levels in 7 days. If levels remain CTCAE Grade <math>\leq</math> 1, then reintroduce erdafitinib.
 
- If resolved in <math>></math> 7 days, then discontinue patient from palbociclib and erdafitinib
 
 
 

Grade 4	Discontinue palbociclib and erdafitinib.

AST or ALT and Bilirubin	
AST or ALT > 3.0 – 5.0 ULN and total bilirubin > 2.0 x ULN	Omit dose of palbociclib and erdafitinib, , and check bilirubin, AST and ALT daily until resolved to CTCAE Grade ≤ 1, then 
 
- If resolved in ≤ 7 days, then ↓ 1 dose level of palbociclib and erdafitinib. Start palbociclib first, and recheck bilirubin, AST and ALT levels in 7 days. If levels remain CTCAE Grade ≤ 1, then reintroduce erdafitinib.
 
- If resolved in > 7 days, then discontinue patient from palbociclib and erdafitinib.
 

AST or ALT > 5.0 ULN and total bilirubin > 2.0 x ULN	Discontinue palbociclib and erdafitinib.
Metabolism and nutrition disorders (for erdafitinib only)	
Phosphorus elevationa	
5.5-6.9 mg/dL	Maintain dose level of erdafitinib. May consider sevelamer 800 mg to 1,600 mg 3 times a day (with food).
7.0-9.0 mg/dL	Omit erdafitinib.  Sevelamer 800 to 1,600 mg 3 times a day with food until phosphate level is <5.5 mg/dL.  Once serum phosphate level returns to <5.5 mg/dL, restart erdafitinib at same dose level.  A dose reduction may be implemented for persistent hyperphosphatemia (≥7 mg/dL) if clinically necessary
>9.0 mg/dL	Omit erdafitinib.  Sevelamer up to 1,600 mg 3 times a day with food  AND  Acetazolamide 250 mg 2 or 3 times a day only until serum phosphate level returns to <5.5 mg/dL.  Once serum phosphate level returns to <5.5 mg/dL, restart treatment at the first reduced dose level.  A second dose reduction may be implemented if needed or clinically indicated for persistent hyperphosphatemia (≥7 mg/dL) at every cycle
>10.0 mg/dL and/or significant alteration in baseline renal function and/or Grade 3 hypocalcemia	Erdafitinib should be discontinued permanently. (In situations where the subject is having clinical benefit and the investigator and the Study Chair agree that re-starting drug is in the best interest of the subject, the drug may be re-introduced at 2 dose levels lower if appropriate. Follow other recommendations described above.)
aNote: Restriction of phosphate intake to 600 – 800 mg/day is recommended to all subjects in the study	
Ocular toxicity (for erdafitinib only)	
Grade 1	Refer to ophthalmologic exam. If this cannot be performed within 7 days, omit erdafitinib until an exam can be performed.  If no evidence of eye toxicity, continue erdafitinib at same dose level.

	
If keratitis or retinal abnormality are detected, omit erdafitinib until signs and symptoms have resolved; follow specific treatment as per ophthalmologist's recommendations.
 
For retinal pathology perform OTC as appropriate and consider referral to a retina specialist for further evaluation.
 
If toxicity is reversible (complete resolution or stabilization and asymptomatic) in 4 weeks according to ophthalmologic exam, resume erdafitinib at the next lower dose level after consultation with Protocol Chair.
 
Monitor for recurrence every 1 to 2 weeks for a month and as clinically appropriate thereafter. If there is no recurrence then re-escalation can be considered in consultation with the medical monitor.
 
If there is no evidence of eye toxicity, continue erdafitinib therapy at the same dose level.

Grade 2	
Immediately omit erdafitinib and refer to ophthalmologic exam.
 
If keratitis or retinal abnormality are detected, omit erdafitinib until signs and symptoms have resolved; follow specific treatment as per ophthalmologist's recommendations.
 
For retinal pathology perform OTC as appropriate and consider referral to a retina specialist for further evaluation.
 
Monitor for recurrence every 1-2 weeks for a month and as clinically appropriate thereafter.
 
If toxicity is reversible (complete resolution or stabilization and asymptomatic) in 4 weeks according to ophthalmologist exam, resume erdafitinib at the next lower dose level if patient is deriving clinical benefit from treatment, after consultation with Protocol Chair.

Grade 3	
Immediately discontinue erdafitinib, refer to ophthalmologic exam, report as SAE.
 
If keratitis or retinal abnormality are detected, omit Erdafitinib until signs and symptoms have resolved; follow specific treatment as per ophthalmologist's recommendations.
 
For retinal pathology perform OTC as appropriate and consider referral to a retina specialist for further evaluation.
 
If toxicity is reversible (complete resolution or stabilization and asymptomatic) in 4 weeks according to ophthalmologist exam, resume erdafitinib at 2 lower dose levels if patient is deriving clinical benefit from treatment, after consultation with Protocol Chair.
 
Continue to monitor for recurrence of toxicity every 1-2 weeks for a month and as clinically appropriate thereafter, using appropriate investigations. For cases of recurrence, permanently discontinue erdafitinib.

Grade 4	
Immediately discontinue erdafitinib permanently, refer to ophthalmologic exam, report as SAE.
 
Continue to monitor for recurrence of toxicity every 1-2 weeks for a month and as clinically appropriate thereafter, using appropriate investigations.

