	
participating in the expansion cohort of the trial (not necessary in the escalation cohort)
 

○ Evaluable (may have either measurable or non-measurable disease)

● Patients must have available tissue (archival formalin-fixed paraffin embedded (FFPE) blocks or fresh frozen biopsy from primary tumor or metastatic tumor biopsy) for correlative studies. Tissue source needs to be located and available at the time of registration (tissue needs to be submitted within 3 weeks of study initiation). Patients will not be able to start study drugs without tissue availability. Submission of tissue can be waived, if approved by the Study Chair in case of extraordinary/catastrophic circumstances.

● Current use of any of the drugs listed on the Cautionary Concomitant Medications list has to be approved by the Study Chair

● Patient must have had at least one line of therapy in the metastatic setting

● Patients must have adequate hematologic, hepatic, and renal function. All laboratory tests must be obtained within 2 weeks from study entry. These include:

○ ANC <math>\geq</math> 1,500/mm^3

○ Platelet count <math>\geq</math> 100,000/mm^3

○ HgB <math>\geq</math> 9.0 g/dL

○ Creatinine clearance <math>\geq</math> 40 mL/min/1.73 m^2

○ SGOT, SGPT <math>\leq</math> 2.5 x ULN if no liver metastasis present

○ SGOT, SGPT <math>\leq</math> 4 x ULN if liver metastasis present

○ Albumin <math>\geq</math> 2.0 g/dL

○ Total serum bilirubin <math>\leq</math> 1.5 x ULN (<math>\leq</math> 3 x ULN or direct bilirubin <math>\leq</math> 1.5 x ULN if known Gilbert's syndrome)

○ Potassium within institutional normal limits

○ Phosphorus <math>\leq</math> institutional upper limit of normal

 
Exclusion Criteria (abbreviated)
 

● Prior use of an FGFR inhibitor

● More than 2 lines of chemotherapy in the metastatic setting. There is no limit on endocrine therapy lines

--	--

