**Notes:**

- Additional tests may be performed at the discretion of the treating investigator as clinically indicated. The sample collection schedules outlined above are based on an ideal subject.
- All appointment/procedures may be performed ± 3 days to accommodate unexpected scheduling issues, weekends and holidays.** The sample schedule should be followed as closely as is realistically possible; however, the schedule may be modified due to problems such as scheduling delays or conflicts (e.g., clinic closure, poor weather conditions, vacations, etc.).
- Shaded cells (gray) represent **RESEARCH** procedures; white cells represent **STANDARD OF CARE** procedures

- Pre-study assessments should be performed within 28 days prior to starting treatment, unless otherwise noted. Please note that the labs obtained on Cycle 1, Day 1 also need to meet eligibility criteria. Screening procedures (i.e. history and physical exam, etc.), excluding labs, which are conducted within 1 week of C1D1 do not need to be repeated. Labs performed on C1D1 for screening are permitted given that they are submitted to the Coordinating Center and approved prior to study treatment initiation.
- Chemistry includes measurement of sodium, potassium, chloride, bicarbonate, BUN, creatinine, glucose, total bilirubin, calcium, total protein, albumin, AST, ALT, and alkaline phosphatase.
- CT scans (chest/abdomen/pelvis) are acceptable for tumor evaluations. MRI of the brain is to be performed only at the discretion of treating physician. Baseline scans should be performed up to 4 weeks prior to study drugs initiation. The scans may be performed ± 5 days of patient's scheduled appointment, to accommodate weekends and holidays
- FFPE blocks may be from the primary tumor (time of original diagnosis) or a metastatic biopsy site. If available, a previously stored fresh-frozen tissue will also be collected. Tissue collected should be submitted at the time of registration. If patients are agreeable, at any time prior, during, or after study drug exposure, an optional (but encouraged) fresh-frozen tissue research biopsy of a metastatic site of disease will be performed and collected (see Section 10.3 for more details). It is assumed that about 20% patients will agree to a fresh biopsy.
- Pill Diary dispensed with study drug for all patients in the study.

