### 7.4 Definition of Dose-Limiting Toxicity (DLT)

Any of the following events that occur during cycle 1 (first 4 weeks) will be considered a DLT when classified as possibly, probably or definitively related to investigational study treatment (according to NCI CTEP Adverse Event Reporting Requirements). Apart from the criteria listed below, if a lower grade AE leads to a dose interruption of more than 21 consecutive days of erdafitinib for the first 4 weeks of Cycle 1, this AE will be considered a DLT; patients must receive at least 75% of study drug during cycle 1 in order to be evaluable for the DLT observation period. Whenever a patient experiences toxicity that fulfills the criteria for a DLT, treatment with the study drug responsible for the toxicity will be interrupted (patient may continue the remainder study drugs) and the toxicity will be followed up. The Protocol Chair must be notified immediately of any DLT:

TOXICITY	DLT CRITERIA
Blood and lymphatic system disorders	Anemia CTCAE Grade $\geq$ 3 will not be considered DLT unless judged to be a hemolytic process secondary to erdafitinib.
	Febrile neutropenia CTCAE Grade $\geq$ 3
	ANC CTCAE Grade 3 for > 14 consecutive days
	ANC CTCAE Grade 4
	Platelet count CTCAE Grade 3 for > 7 consecutive days and/or with signs of bleeding
	Platelet count CTCAE Grade 4
Ocular disorders	CTCAE Grade $\geq$ 2 for > 21 days CTCAE Grade $\geq$ 3
General disorders and administration site conditions	Fatigue CTCAE Grade 3 for > 7 consecutive days
Skin and subcutaneous tissue disorders	Skin, mucosal or nail toxicity CTCAE Grade $\geq$ 3 for > 72 hours
Hyperphosphatemia	Phosphorus level $\geq$ 7.0 mg/dL for > 14 days despite treatment
GI disorders a	Diarrhea CTCAE Grade $\geq$ 3 for $\geq$ 48 hrs, despite the use of anti-diarrhea therapy
	Nausea/vomiting CTCAE Grade $\geq$ 3 for $\geq$ 48 hrs, despite the use of anti-emetic therapy
	Constipation CTCAE Grade $\geq$ 3 for $\geq$ 48 hrs, despite the use of anti-constipation therapy
Investigations b	Blood bilirubin c CTCAE Grade 2 for > 7 consecutive days or $\geq$ Grade 3
	AST or ALT CTCAE $\geq$ Grade 3
	Alkaline phosphatase CTCAE $\geq$ Grade 3
Other hematologic and non-hematologic toxicities	Any other CTCAE $\geq$ Grade 3 toxicity for > 7 consecutive days (except decreased lymphocyte count [lymphopenia] that is not clinically significant)

TOXICITY	DLT CRITERIA

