Renal	If creatinine $\geq 2 \times$ ULN has been demonstrated, this parameter must be evaluated at least twice a week until resolution to $\leq$ CTCAE grade 1 to allow for initiation of re-treatment, and then at least weekly until either resolution or until stabilization.  Creatinine $\geq 2.0 \times$ ULN and 3+ proteinuria or hematuria $\geq$ CTCAE grade 2 has been demonstrated, a 24-hour urine collection for total protein and total creatinine must be repeated at least weekly until either parameter returns to baseline value or until stabilization. Whenever a measured CrCl is obtained, a creatinine should be obtained within $\leq 72$ h of the urine collection.
Hepatic	If total bilirubin $\geq 2 \times$ ULN or $\geq$ CTCAE grade 3 AST/ALT has been demonstrated, these parameters must be repeated daily until resolution to $\leq$ CTCAE grade 1 (or $\leq$ grade 2 for AST or ALT, if liver metastasis are present) to allow for initiation of re-treatment, and then at least weekly until either resolution or until stabilization  Patients with total bilirubin $>$ ULN (any duration) should have fractionation of bilirubin into total/direct or indirect/direct components and any additional work-up as clinically indicated by

	these results. Follow-up of hyperbilirubinemia should proceed as per the guidelines above, irrespective of the results of fractionation.
Metabolic/Laboratory	Parameters of metabolic/ laboratory abnormalities $\geq$ CTCAE grade 3 must be assessed once at 2 to 4 days and once again at 7 days ( $\pm 1$ day) and be repeated twice a week until resolution to $\leq$ CTCAE grade 2 to allow for initiation of re-treatment, and then at least weekly until either resolution to $\leq$ CTCAE grade 1 or until stabilization.
	A CT scan or other imaging study to assess the pancreas, liver, and gallbladder must be performed within 1 week of the first occurrence of any $\geq$ CTCAE grade 3 of amylase or lipase levels.
	In patients with triglycerides $\geq 500$ mg/dL, urine amylase needs to be tested in addition.
Ocular toxicity	Patients who experience ocular toxicity should be followed as per Dose Modification guidelines (Section 8)
Non-Laboratory	Patients who experience non-laboratory DLTs must be evaluated at least once a week following demonstration of the toxicity until resolution of the toxicity to allow for re-treatment, stabilization of the toxicity, or study treatment completion.

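### The AST/ALT hold, restart and erdafitinib reintroduction rules for patients with liver metastases do not agree with each other or with the 4 x ULN entry limit

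*Combined protocol and SAP*

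**What the plan says.** **Entry.** The synopsis and 4.1.10e cap AST/ALT at 2.5 x ULN without liver metastases; with them the cap is "4 x ULN if liver metastasis present". The first numbered note to the Study Calendar (Section 6) adds: "Please note that the labs obtained on Cycle 1, Day 1 also need to meet eligibility criteria".

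**Section 8.4, AST or ALT, Grade 2.** The instruction is "Omit dose of palbociclib and erdafitinib, and check AST and ALT daily until resolved to CTCAE Grade" 1 or below. Neither liver metastases nor baseline is mentioned.

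**Section 8.4, AST or ALT, Grade 3.** Both drugs are held until Grade 1 or below, or until Grade 2 or below "in case of liver metastasis), then". If this takes 7 days or less, both drugs drop one level and palbociclib starts first. AST and ALT are rechecked after 7 days, and erdafitinib returns only if they are still at Grade 1 or below. If it takes longer, both drugs stop.

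**Section 7.4.** The hepatic follow-up row, triggered on AST/ALT at Grade 3 or above, accepts "grade 2 for AST or ALT, if liver metastasis are present) to allow for initiation of re-treatment". Footnote b of the DLT table, on when to image the abdomen, makes a similar allowance for tumor in the liver. The DLT line is "AST or ALT CTCAE $\geq$ Grade 3", with no baseline wording.

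**Section 7.5.** Dose reduction is required for Grade 2 or higher AST/ALT lasting more than 14 days, with no mention of attribution, baseline or liver metastases. Section 17.2.1 has a similar trigger at more than 2 weeks.

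**The concern.** There are two separate problems.

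First, the entry limit and the Grade 2 hold appear to overlap. If they do, some patients who are properly enrolled start treatment at a grade for which the table prescribes a hold, and the hold ends only at a level better than the one they came in with. Other provisions do adapt. The Grade 3 row and the 7.4 hepatic row accept Grade 2 with liver metastases, and the mucositis row and the nail Grade 2 and 3 rows accept a return to baseline. The Grade 2 AST/ALT row does neither.

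Second, the Grade 3 row is at odds with itself and with the row above it.

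The stake is more than dosing. Holds feed the Cycle 1 DLT evaluability rule, the rules that turn a long erdafitinib interruption into a DLT, and the 8-week tolerability count behind the recommended phase II dose. If sites resolve the conflict differently, these counts depend on which line was followed.

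**Working it through.** There is no planned figure to reproduce; this is a comparison of thresholds.

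**1. Overlap of eligibility and Grade 2.** Section 13.1 adopts CTCAE v4.03, but the documents do not print its AST/ALT cut-offs. The band above 3.0 to 5.0 x ULN is printed only in the combined AST/ALT-and-bilirubin row of 8.4, without a grade label. I take it as Grade 2, as an assumption.

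- No liver metastases: ceiling 2.5, Grade 2 floor 3.0, no overlap.
- Liver metastases: ceiling 4.0, Grade 2 floor 3.0, overlap 4.0 − 3.0 = 1.0 x ULN.

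| Assumed start of Grade 2 (above) | Overlap with the 4 x ULN ceiling |
|---|---|
| 2.5 x ULN | 1.5 x ULN |
| 3.0 x ULN | 1.0 x ULN |
| 3.5 x ULN | 0.5 x ULN |
| 4.0 x ULN | 0 |

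The overlap disappears only if Grade 2 starts at 4.0 x ULN or higher.

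**2. What restart asks of such a patient.** Grade 1 or below means at most 3.0 x ULN on the same assumption. From a baseline of 4.0 x ULN, that is a fall of (4.0 − 3.0)/4.0 = 25% below the patient's own baseline.

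**3. The Grade 3 row, with no cut-off assumed.** Take a patient with liver metastases whose Grade 3 value falls to Grade 2 within 7 days.

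- The Grade 3 row ends the hold and starts palbociclib.
- The Grade 2 row says that both drugs are held at that grade.
- Erdafitinib returns only if levels are still at Grade 1 or below at the recheck. The patient was at Grade 2 when the hold ended, so there is no Grade 1 level to maintain.

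In the Grade 2 row the same recheck wording is coherent, because that hold already ends at Grade 1 or below.

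**4. What a hold does to Cycle 1.** Section 7.4 requires at least 75% of study drug in Cycle 1 for DLT evaluability.

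- Erdafitinib, 28 planned doses: 7 missed leaves 21/28 = 75.0%; 8 missed leaves 20/28 = 71.4%.
- Palbociclib, 21 planned doses: 5 missed leaves 16/21 = 76.2%; 6 missed leaves 15/21 = 71.4%.

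Section 7.4 also says that a lower-grade event interrupting erdafitinib for more than 14 consecutive days may be a DLT, and for more than 21 days in Cycle 1 is one. For an uninterrupted erdafitinib hold due to a related lower-grade event:

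| Days held in Cycle 1 | Reading under 7.4 |
|---|---|
| up to 7 | evaluable on the 75% rule |
| 8 to 14 | below 75%, no interruption DLT |
| 15 to 21 | below 75%, DLT at discretion |
| 22 or more | DLT |

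A hold from Day 8 through Day 28 misses 21 doses, so it falls in the discretionary class. One DLT in a cohort of three moves the decision in Table 17.2.1 from E (0/3) to S (1/3). A hold of 8 to 14 days would instead cost an evaluable patient. The two routes do not point the same way.

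**5. How many patients.** The documents give neither the share with liver metastases nor the share entering above 3 x ULN. Purely for illustration, with 30–50% and 5–10% assumed for these, the count at entry runs from 26 × 0.30 × 0.05 = 0.4 to 35 × 0.50 × 0.10 = 1.8. The conflict in step 3 is not limited to them: it can reach any patient with liver metastases who has a Grade 3 rise that returns to Grade 2.

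**The case against.** The best reply is that the table is not meant for unchanged baseline values. Section 8.3.2 introduces it for significant treatment-related toxicity. Section 13.2.1 includes among adverse events what is new or worse than baseline, and 13.3.1 has a pre-existing condition reported only if it worsens. A DLT under 7.4 must be at least possibly related to treatment. Section 8.5 lets the Protocol Chair approve departures in advance, and the 28-day discontinuation rule in 8.4 is aimed at delays that stem from the study. A stricter bar for bringing back the second drug may also be deliberate.

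Much of this stands. A reader might infer that unchanged, tumor-related values stop both drugs at the first on-treatment lab or are scored as a hepatic DLT. Read together, these provisions do not support that. Nor would 7.4 re-dose the Grade 2 patient whom 8.4 holds, because its AST/ALT trigger is Grade 3. From 4.0 x ULN a 25% rise reaches 5.0 x ULN, the top of the assumed Grade 2 band, but that follows from any ULN-based grading and is no error in itself.

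The reply does not settle the rest. The Grade 2 row is keyed to absolute grade, and 7.5 carries no attribution or baseline wording. A rise judged treatment-related but still within Grade 2 leads to a restart level below baseline. A staged return of erdafitinib could explain a stricter second bar, but not a row that restarts palbociclib at a grade where the row above holds it. Case-by-case approval leaves the contradiction in the text.

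**Conclusion.** The point holds in two parts. The Grade 3 inconsistency follows from the printed text alone. The overlap of eligibility with the Grade 2 hold rests on Grade 2 starting below 4.0 x ULN. It concerns only patients with liver metastases who enter above that start, above 3.0 and up to 4.0 x ULN on the assumed band. For them the problem is a treatment-related change, since an unchanged baseline value may well be exempt.

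The number affected at entry is probably small and cannot be derived from the documents. A reader might infer that the DLT rate, the MTD and the tolerability count are biased toward toxicity. That is not shown: a hold can add a DLT, remove an evaluable patient or do neither, depending on its length and attribution. The wording should be corrected because it governs dosing and feeds the primary endpoint, but it is not an essential correction on which the design stands or falls.

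**What to change.** Reconcile 4.1.10e, the 7.4 hepatic row, 7.5 (with its counterpart in 17.2.1) and the AST/ALT Grade 2 and Grade 3 rows of 8.4 into one consistent rule for patients with liver metastases. It should cover the hold, the end of the hold and the reintroduction of erdafitinib. State explicitly how AST/ALT values already raised at baseline are treated, both for holds and for the AST/ALT DLT line. Print the grade cut-offs being used, so that the overlap with eligibility can be seen. The clinical thresholds are for the sponsor to choose.

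The cost is a wording amendment in these sections. No new tests are needed, since AST and ALT are already scheduled. The drawback is slightly more complex wording for patients with liver metastases.
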